8.5. ACCOUNTABILITY OF RZL-012 AND VEHICLE

The RZL-012 investigational product was manufactured by PharmaCore (USA) and complies with cGMP requirements. Formulation and packing were done by Nextar (Israel) and complies with cGMP requirements.

The vehicle was manufactured and packed by Nextar (Israel) and complies with cGMP requirements.

The RZL-012 investigational product and vehicle will be supplied in kits, in quantities as needed to comply with the treatment of site subjects according to the study protocol.

Site coordinator will notify the Sponsor or its official designee, in a timely manner and no less than 14 working days in advance, of any supply requirements to prevent shortage.

Shipment, storage and inventory documentation will be updated regularly and kept in the investigation files at the site to allow inspection and trace of the supplied product.

9. ADVERSE EVENTS

9.1. ADVERSE EVENT DEFINITIONS

9.1.1. Definition of AE

An AE is defined as any untoward medical occurrence in a clinical investigation subject administered a pharmaceutical product and which does not necessarily have to have a causal

relationship with this treatment. An AE can therefore be any unfavorable and unintended sign (including an abnormal laboratory finding, for example), symptom, or disease temporally associated with the use of a medicinal product, whether or not considered related to the medicinal product. This definition includes any abnormalities or anomalies that were not seen at baseline or which worsened during the course of the study, if present at baseline.

9.1.2. Definition of Serious Adverse Event

A SAE is defined as any AE occurring at any dose that results in any of the following outcomes:

- death
- a life-threatening AE, as defined below
- subject hospitalization or prolongation of existing hospitalization
- a persistent or significant disability/incapacity
- a congenital anomaly/birth defect
- important medical event, as defined below

A life-threatening AE is any AE that places the subject, in the view of the investigator, at immediate risk of death from the reaction as it occurred (i.e., it does not include a reaction that, had it occurred in a more severe form, might have caused death).

An important medical event is an AE that may not result in death, be life-threatening, or require hospitalization but may be considered a serious AE when, based upon appropriate medical judgment, may jeopardize the subject and may require medical or surgical intervention to prevent one of the outcomes listed above. It can also include AEs otherwise judged to be serious by either the investigator or the Sponsor.

9.1.3. Definition of Adverse Drug Reaction

AEs associated with the use of investigational product (i.e., probably or possibly related to treatment as defined in Section 9.3) are also termed ADRs.

9.2. ADVERSE EVENT GRADING

AE will be documented in each study visit.

AEs severity will be graded as follows:

• Mild: Sign or symptom, usually transient, requiring no special treatment and generally not interfering with usual activities.

- Moderate: Sign or symptom, which may be ameliorated by simple therapeutic measures, may interfere with usual activity.
- Severe: Sign or symptom that is intense or debilitating and that interferes with usual activities and/or requires hospitalization. Recovery is usually aided by therapeutic measures and the discontinuation of the study product may be required.

9.3. CAUSALITY ASSESSMENT OF ADVERSE EVENTS

All AEs will be evaluated by the investigator and assigned an estimated relationship to the RZL-012 investigational product. The terms "related" or "non-related" refer to the association with the use of the investigational product, as defined below in Table 8.

Medical judgment should be used to determine the relationship, considering all relevant factors, including pattern of reaction, temporal relationship, confounding factors such as concomitant medication, concomitant diseases and relevant history.

Assessment of causal relationship should be recorded directly in subjects' CRF.

Definition of AEs causality is specified in the table below. (Table 8).

 Table 8: Definition of Causality

TERM	DEFINITION
	This category applies to those AEs which, after careful consideration, are clearly due to extraneous causes (disease, environment, etc.)
	This category applies to those AEs which, after careful medical consideration at the time they are evaluated, are felt with high degree of certainty to be related to the study procedures/investigational product.

9.4. ADVERSE EVENT REPORTING AND MONITORING REQUIREMENTS

9.4.1. General

All AEs, serious and non-serious, will be fully documented in both source documents and CRFs as described in Section 5.1.14, and each AE will be assessed in light of its clinical significance. For each AE, the investigator will provide the onset, end, intensity, treatment required, outcome, seriousness and action taken with the investigational drug. The investigator will determine the relationship to the investigational drug, i.e., causality assessment, for each AE.

Any AE occurring prior to initiation of first dose, after initiation of the first dose and or during any point throughout the study should be recorded on the AE page of the CRF. All AEs occurring until subject is terminated from the study (84 days after the injection of RZL-012), should be captured in the CRF. AEs should be recorded in the CRF using the medical

terminology found in the source documentation. Whenever possible, diagnoses should be given when signs and symptoms are due to a common etiology.

Occurrence of any serious or severe ADR must warrant clinical evaluation by the treating investigator and reported to the Sponsor/medical monitor within 24 hours.

ADRs will be followed-up until resolution, or for a maximal duration of 6 months after RZL-012 injection, whichever occurs first.

9.4.2. SAE Reporting

The PI or his designee must report to the Sponsor any SAE occurring after injection of the study treatment, regardless of their relationship to the investigational product.

Sponsor contact details for SAE reporting:

[name], [contact] or [contact].

An initial report must be faxed or emailed to [contact] or [contact] within 24 hours of becoming aware of the event and must include SAE general description, start date, end date (if applicable), the reason for evaluation as a SAE, basic subject information, assessment of the relationship to the investigational product, expectedness, and study therapy information.

Follow-up information, including outcome and treatment, shall be faxed or emailed within 48 hours. Source documents to support the SAE (e.g., discharge summary, test results) shall be included in the report.

A complete SAE report must be sent to the Sponsor at the first possible date and no later than 7 calendar days after SAE end date. In addition to the information described in the initial report, this report will include AEs description and grading, treatment given (if applicable), SAE outcome, an assessment of the relationship to the investigational product, and expectedness.

SAE will be recorded on designated CRF forms in a timely manner and no later than 7 calendar days after its end date.

The PI or his designee will submit the SAE report to IRB/EC according to applicable local regulations and will update the Sponsor.

10. STATISTICAL CONSIDERATIONS

10.1. STUDY DESIGN AND OBJECTIVE

The statistical analysis described below relates to the place-controlled phase of the study.

This study will be a double blinded, randomized, placebo-controlled, Phase 2b trial to assess RZL-012 efficacy on DD subjects. A total of 38 eligible subjects will be randomized to receive a single injection session with either RZL-012 or placebo (vehicle) in a 1:1 ratio and will be monitored for safety and efficacy during 84 days of follow up.

Once study ends and codes opened, the 19 placebo-treated subjects will be offered to be treated with RZL-012 and followed up for an additional 84 days. The efficacy and safety results that will be collected during the open label extension phase of the study will be reported in a separate statistical report.

Primary end point:

Average percent reduction in lipoma/nodule height on day 84 after injection vs baseline, in the RZL treated group as compared to the placebo treated group. Lipoma height will be assessed by ultrasound.

Key secondary Endpoint:

Average percent reduction in lipoma/nodule pain on day 84 after injection vs baseline, in the RZL-012 treated group as compared to the placebo treated group. Lipoma pain will be assessed by the Comparative Pain Scale.

Additional secondary endpoints:

- 1. RZL-012 injection safety and tolerability in DD subjects.
- 2. Percent responding lipomas/nodules (a responding lipoma is defined as having more than 75% height reduction on day 84 after injection vs baseline), in the RZL-012 treated group as compared to the placebo treated group.

10.2. STUDY ENDPOINTS

10.2.1. Analysis of Efficacy for Primary Endpoint

• Analysis per patient (based on 4-8 lipomas/nodules per patient)

The two-sample T-test or Non-parametric Wilcoxon-Mann-Whitney Rank sum test for independent samples (as is appropriate) will be applied for testing the statistical significance of the difference between study groups in percent reduction of lipoma/nodule height at day 84 after injection vs. baseline.

Analysis of covariance (ANCOVA) model will be applied in order to identify covariate parameters suspected as related to reduction in lipoma/nodule height and in order to test the differences in percent reduction of lipoma/nodules height between the treatment groups adjusted to the above covariates.

• Analysis per lipoma/nodule (based on 4-8 lipomas/nodules per patient)

The MMRM model (Mixed-effect model for repeated measures) will be applied for analyzing the difference between the groups in percent reduction of lipoma/nodule height from baseline to day 84 and adjusted for the above covariates as appropriate.

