5.1.13. Imaging: Ultrasound (US)

Evaluation of Ultrasound will be conducted at Screening (performed 14 through 1 days prior to baseline) to ensure compliance with study inclusion criteria and establishing a baseline. Nodule size and tissue characteristics will be documented. Additional US will be performed on Day 0. In case of screening visit that will be conducted only one day before Baseline, ultrasound and photographs at Baseline visit are optional. The ultrasound parameters and phots collected at screening will be used at Baseline visit. In case the study personnel decide to inject different lipomas than those that were chosen at the screening visit, then ultrasound evaluation is mandatory on Day 0. Additional US measurements for the injected lipomas will be done at Days 28, 56 and 84 visits and the change in dimensions will be compared to the recorded dimensions at baseline.

Ultrasound imaging will be conducted on Day 0 (before injection) in order to ensure proper dose injection according to measured nodule size/diameter. In case of screening visit that will be conducted only one day before Baseline, ultrasound and photographs at Baseline visit are optional. The ultrasound parameters collected at screening will be used at Baseline visit.

Assessment of nodular size will be by diameter (mm) and surface (mm²) in three dimensions as illustrated below:

- Height
- Width
- Length

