10.3. SAMPLE SIZE JUSTIFICATION

Based on primary endpoint:

The rationale for sample size calculation was based on interim data from Raziel's open label phase 2a study (Study #RZL-012-FD-P2aUS-001) in which reduction in lipoma/nodule height of about 55% was demonstrated in the treatment group. Raziel's phase 2a study did not include a placebo group but studies reported by other groups (15,16) show an average reduction from baseline in lipoma/nodule height of about 7% in the placebo group. Taking these numbers into consideration Raziel expect an effect size of 0.96 (effect size = expected effect size in treated (0.55) – expected effects size in placebo group (0.07)/expected standard deviation (0.5)).

Sample size justification:

A sample size of 19 in each group (total sample size of 38) will have 80% power to detect a difference in means of 48 (the difference between a Group 1 mean, μ 1, of 55 and a Group 2 mean, μ 2, of 7) assuming that the common standard deviation is 50 using a two-group t-test with a 0.05 two-sided significance level.

Based on key secondary endpoint:

The rationale for sample size calculation was based on data from our open label phase 2a study (Study #RZL-012-FD-P2aUS-001) in which reduction in lipoma/nodule pain score of about 76% was demonstrated in the treatment group. Our phase 2a study did not include a placebo group but pain studies reported by other groups (17) show a range of reduction in pain score from +10% - 60% in the placebo group. Based on Geography, study size and length we selected an expected reduction from baseline of 25% in lipoma pain in our placebo group. Taking these numbers into consideration we expect an effect size of 1.02 (effect size = expected effect size in treated (0.76) – expected effects size in placebo group (0.25)/expected standard deviation (0.5)).

Sample size justification:

A sample size of about 19 in each group (total sample size of 38) will have 80% power to detect a difference in means of 51 (the difference between a Group 1 mean, μ 1, of 76 and a Group 2 mean, μ 2, of 25) assuming that the common standard deviation is 50 using a two-group t-test with a 0.05 two-sided significance level.

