10.4. STATISTICAL ANALYSIS

10.4.1. General

All measured variables and derived parameters will be listed individually and, if appropriate, tabulated by descriptive statistics.

For categorical variables summary tables will be provided giving sample size, absolute and relative frequency and 95% CI (Confidence Interval) for proportions by study group.

For continuous variables summary tables will be provided giving sample size, arithmetic mean, standard deviation, coefficient of variation (CV%), median, minimum and maximum and 95% CI (Confidence Interval) for means of variables by study group.

All tests will be two-tailed, and a p value of 5% or less will be considered statistically significant.

Subject Disposition

A detailed description of subject accountability including count of subjects included, exposed, completed (i.e., subjects who complete the study treatment) and discontinued along with the main reason for discontinuation will be generated for each treatment group and for all subjects. All withdrawals from the study, taking place on or after study drug injection, will be fully documented in the body of the Clinical Study Report.

Note that the actual study duration is for a period of maximum 3.5 months, with efficacy analyses being conducted at Day 28, 56, and 84 visits.

At the end of the period, when the follow up of subjects will be completed, randomization codes will be opened.

Placebo subjects who would like to be treated with RZL-012 at the end of the study will be injected (within a period of 30 days from codes opening) and will be followed up for efficacy for additional 84 days. The efficacy information that will be collected for the open label extension study will not be included in the randomized double blinded study report but will be used for internal information.

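### Section 10.2.1 tests the primary endpoint several ways at 5%, one of them with covariates identified in the trial data, and names none as the decision analysis

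*Combined protocol and SAP*

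**What the plan says.** Section 10.2.1 sets out the primary efficacy analysis under two headings, per patient and per lipoma.

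- **Per patient, simple comparison:** "The two-sample T-test or Non-parametric Wilcoxon-Mann-Whitney Rank sum test for independent samples (as is appropriate) will be applied for testing the statistical significance". The parenthesis is the only guidance on choosing between the two tests.
- **Per patient, adjusted:** "Analysis of covariance (ANCOVA) model will be applied in order to identify covariate parameters suspected as related to reduction in lipoma/nodule height". The same sentence gives the model a second job, "in order to test the differences in percent reduction of lipoma/nodules height between the treatment groups adjusted to the above covariates". No covariate is listed.
- **Per lipoma:** an MMRM for "percent reduction of lipoma/nodule height from baseline to day 84 and adjusted for the above covariates as appropriate". The visits that enter it are not stated.

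None of these is called primary, supportive or sensitivity. The synopsis carries the same list, and section 10.2.2 repeats it for pain. Section 10.4.1 states: "All tests will be two-tailed, and a p value of 5% or less will be considered statistically significant". Section 10.4.3 (Efficacy Analysis) adds only tables. Section 10.3 sizes the trial "assuming that the common standard deviation is 50 using a two-group t-test with a 0.05 two-sided significance level".

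**The concern.** A trial with one primary endpoint, a powered sample size and a 5% rule needs one identified p-value. Here at least three analyses can each produce a significance statement about the same comparison, and the text does not say which leads if they differ. Even the simple patient-level comparison is open between two tests.

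The ANCOVA is the weakest element as written. A search for covariates that predict the outcome is harmless as a labelled exploration. Section 10.2.1 also uses the resulting model to test treatment at 5%, so the adjustment set, and with it the p-value, depends on the outcome data.

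**Working it through.** **1. The plan's own figure.** Inputs from section 10.3: means 55 and 7, SD 50, 19 per arm, two-sided 0.05, t-test.

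- Effect size: (55 − 7)/50 = 0.96.
- Noncentrality: 0.96 × √(19/2) = 2.96, with 19 + 19 − 2 = 36 degrees of freedom.
- Power (noncentral t): 82.1% at 19 per arm and 79.9% at 18. The smallest n reaching 80% is 19, so the stated size reproduces.
- Pain: (76 − 25)/50 = 1.02, giving 86.4% at 19 per arm.

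**2. Is a decision analysis named anywhere?** Sections 10.2.1, 10.2.2, 10.3, 10.4.1 and 10.4.3 and the synopsis were set side by side. Two pointers favour the patient-level test: the t-test in the sizing, and the statistical-significance wording attached to the t-test or Wilcoxon. The first is a planning assumption. The second is matched by the ANCOVA, which is also there to test the group difference. Neither designates an analysis.

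**3. Error rate when there is no treatment effect (simulation).** From the documents: 19 per arm and 4 to 8 lipomas per patient. Assumed, because the documents give no values: normal data, within-patient correlation 0.2 or 0.5, and 2 to 6 candidate covariates unrelated to outcome, kept at p<0.10. The t-test and ANCOVA rows come mainly from runs of 40,000 trials per scenario (Monte Carlo error about 0.12 points). The combined row comes mainly from runs of 15,000 (about √(0.06 × 0.94/15,000) = 0.2 points).

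| Analysis | Rejects at 5% |
|---|---|
| t-test alone | 4.9–5.2% |
| Covariate-search ANCOVA, screened with treatment in the model | 5.3–6.5% |
| Covariate-search ANCOVA, screened without treatment | 5.0–5.2% |
| Either t-test or covariate-search ANCOVA | 5.3–6.8% |

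The plan does not say which way covariates would be screened.

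**4. Power if one baseline covariate is fixed in advance.** Simulated ANCOVA, 400,000 trials per cell, 19 per arm, 38 − 3 = 35 degrees of freedom, normal data. The baseline–outcome correlation r is assumed.

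| r | Height (t-test 82.1%) | Pain (t-test 86.4%) |
|---|---|---|
| 0 | 80.9% | 85.4% |
| 0.1 | 81.3% | 85.7% |
| 0.2 | 82.4% | 86.7% |
| 0.3 | 84.4% | 88.4% |
| 0.5 | 90.5% | 93.5% |

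At r = 0 the loss is 82.1 − 80.9 = 1.2 points for height and 86.4 − 85.4 = 1.0 for pain. Break-even lies between r = 0.1 and r = 0.2.

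**The case against.** The sponsor's best answer is that the intent can be read. The patient-level test is listed first, the sizing uses a t-test, and choosing between t and Wilcoxon by a look at the distribution is ordinary practice. That choice need not inflate error. With an assumed Shapiro-Wilk rule at 0.05 on residuals (20,000 null trials), the two-step procedure rejected in 5.2% of trials with normal data and 4.7% with skewed data. This stands: the open choice is a gap in specification, not a demonstrated source of false positives. It still leaves the test unnamed, and no check, threshold or timing is given.

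The suspected covariates could also mean factors suspected beforehand. That is possible, but the text says the model is applied to identify them, and no list exists.

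Normal data is a weak assumption for these endpoints. With the plan's means and SD, normality puts 18% of treated patients above 100% height reduction ((100 − 55)/50 = 0.90) and 32% above 100% pain reduction ((100 − 76)/50 = 0.48). Neither is possible, so the simulated figures are indicative only.

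A reader might infer three stronger points that the documents do not support:

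- **That the MMRM tests one effect over all visits.** Section 10.4.1 has a note under Subject Disposition, "with efficacy analyses being conducted at Day 28, 56, and 84 visits", but it defines no model. The contrast in sections 10.2.1 and 10.2.2 is Day 84; only the visits entering the model are open.
- **That success may be claimed on the smallest of all the p-values.** The plan says t-test or Wilcoxon, not both, and the 5% rule sets a significance level, not a success criterion.
- **That lipomas would be analysed as if independent.** The model is called mixed-effect. Its patient effect is unstated, but nothing says it is absent.

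**Conclusion.** The point holds as a gap in pre-specification, together with one method that is weaker than it need be. No text fixes which analysis decides the primary endpoint or the key secondary endpoint, and an ANCOVA with searched covariates is given a treatment test at 5%. The excess error is small: at most about 1.5 points for the covariate-search ANCOVA alone (6.5 − 5.0) and 1.8 points if either it or the t-test is allowed to count (6.8 − 5.0). It is close to nil for that ANCOVA if covariates are screened without treatment. These sizes depend on the assumed number of candidates, screening threshold and normal data. The gap itself does not depend on them, and the sample size is not in question. It should be fixed, but it does not threaten the trial.

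**What to change.** Before the codes are opened, name one decision analysis of the patient-level mean percent reduction at Day 84 that does not change with the data. Either of these closes the gap:

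1. ANCOVA with treatment and baseline mean lipoma height fixed in advance, replacing the covariate search (baseline mean pain in section 10.2.2); or
2. the two-group t-test already used in section 10.3.

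Label the Wilcoxon, any covariate-search ANCOVA and the MMRM as sensitivity analyses, and state which visits enter the MMRM. Carry the same wording into section 10.2.2 and the synopsis.

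The cost is a few sentences. No patients, visits or measurements are added: under section 5.1.13 "the change in dimensions will be compared to the recorded dimensions at baseline", and section 5.1.5 has pain scored for each selected lipoma before injection. Option 1 costs about 1 point of power if baseline is unrelated to outcome, still above the stated 80%, and gains above a correlation of roughly 0.2, a value the documents do not give. Option 2 costs no power. Either way the sponsor gives up the freedom to lead with another analysis.

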5.1.5. Pain Measurement

Local lipoma pain, as determined by the Comparative Pain Scale, will be measured at Baseline visit prior to injection, in order to establish a baseline for comparison following drug injection. Subjects will complete a comparative pain scale score for each lipoma selected for injection.

Additional pain measurements for the treated lipomas will be performed on study visit Days 28, 56, and 84 after injection.

A description of the comparative pain sale is presented in Appendix II.

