10.2.2. Analysis of Efficacy for key secondary Endpoint

• Analysis per patient (based on 4-8 lipomas/nodules per patient)

The two-sample T-test or Non-parametric Wilcoxon-Mann-Whitney Rank sum test for independent samples (as is appropriate) will be applied for testing the statistical significance of the difference between study groups in percent reduction of lipoma/nodule pain at day 84 after injection vs. baseline.

Analysis of covariance (ANCOVA) model will be applied in order to identify covariate parameters suspected as related to reduction in lipoma/nodule pain and in order to test the differences in percent reduction of lipoma/nodules pain between the treatment groups adjusted to the above covariates.

• Analysis per lipoma/nodule (based on 4-8 lipomas/nodules per patient)

The MMRM model (Mixed-effect model for repeated measures) will be applied for analyzing the difference between the groups in percent reduction in local pain score at day 84 vs. baseline between the study groups adjusted for the above covariates as appropriate.

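### The patient-level analyses do not guarantee adjustment for baseline height or pain and do not say which test decides; precision may be forgone, but the stated power is met.

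*Combined protocol and SAP*

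**What the plan says.** Section 10.2.1 opens the per-patient analysis of height with "The two-sample T-test or Non-parametric Wilcoxon-Mann-Whitney Rank sum test for independent samples (as is appropriate) will be applied". Section 10.2.2 does the same for the "difference between study groups in percent reduction of lipoma/nodule pain at day 84 after injection vs. baseline". Neither test contains a baseline term. Section 10.3 builds the sample size on the unadjusted comparison, "using a two-group t-test with a 0.05 two-sided significance level".

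Under the same per-patient bullets, both sections add an ANCOVA with two purposes: to find covariates thought to be related to the outcome, and to test the treatment difference adjusted for them. A per-lipoma MMRM follows, adjusted for the same covariates where appropriate. No covariate is named in either section, and no sentence says which of the t-test, Wilcoxon test, ANCOVA or MMRM decides the endpoint. The statistical section of the synopsis repeats this text.

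Both baseline values are available. Under 5.1.13, ultrasound is done before injection (a screening scan from the day before may serve as baseline), and afterwards "the change in dimensions will be compared to the recorded dimensions at baseline". Under 5.1.5, pain is scored before injection: "Subjects will complete a comparative pain scale score for each lipoma selected for injection".

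**The concern.** Two things are left open that could be closed at almost no cost.

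The first is precision. If percent reduction is related to the baseline value within arms, a model containing that value has a smaller residual variance than the t-test. Expressing the outcome as a percentage of baseline does not guarantee that the relation vanishes, because the denominator is itself a measured value with error.

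The second is the choice of analysis. Baseline height or pain enters the ANCOVA only if the outcome data point to it, and the adjusted and unadjusted results then stand side by side with no rule for which one counts. With 19 patients per arm they can fall on opposite sides of 5%.

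**Working it through.** **Inputs from section 10.3.** 19 per arm; "total sample size of 38) will have 80% power to detect a difference in means of 48" (55 versus 7) for height; "difference in means of 51 (the difference between a Group 1 mean" (76 versus 25) for pain; "assuming that the common standard deviation is 50" for both; two-sided 0.05. The documents give no correlation between baseline and percent reduction, so it is varied here as an assumption ρ.

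**Step 1: reproduce the plan.** For a two-group t-test the noncentrality is λ = (δ/σ)·√(n/2), with 2n − 2 degrees of freedom.

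- Height: λ = (48/50)·√9.5 = 2.96 on 36 df, power 82.1%. At 18 per arm power is 79.9%, so 19 is the smallest number that reaches 80%. The stated figure reproduces.
- Pain: λ = (51/50)·√9.5 = 3.14 on 36 df, power 86.4%. The smallest number for 80% is 17 per arm, so 19 is conservative.

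**Step 2: add one baseline covariate.** The residual SD becomes 50·√(1 − ρ²) and the degrees of freedom fall to 35. Estimating the slope in a trial this small also inflates the variance of the treatment difference by about 1 + 1/(N − 4) = 1 + 1/34, which divides λ by 1.015. Changes in power are given in percentage points against the unadjusted test, without / with this factor.

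| ρ | Residual SD | Height power, no factor | Height change | Pain power, no factor | Pain change |
|---|---|---|---|---|---|
| 0 | 50.0 | 82.0% | about 0 / −1.2 | 86.4% | about 0 / −1.0 |
| 0.1 | 49.7 | 82.4% | +0.3 / −0.8 | 86.7% | +0.3 / −0.7 |
| 0.3 | 47.7 | 85.4% | +3.3 / +2.3 | 89.3% | +2.9 / +2.0 |
| 0.5 | 43.3 | 91.3% | +9.2 / +8.5 | 94.2% | +7.8 / +7.1 |

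The column with the factor is the fairer one at this sample size.

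**Step 3: chance imbalance.** The standard error of the unadjusted difference is 50·√(2/19) = 16.2 points. A one-standard-error imbalance in the baseline mean moves the unadjusted difference by ρ × 16.2: 4.9 points at ρ = 0.3 and 8.1 at ρ = 0.5. This is part of the sampling error that the t-test already allows for, and it is not bias.

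**Step 4: leaving the choice open.** In 20,000 simulated null trials with 19 per arm, counting a trial as positive if either the t-test or a one-covariate ANCOVA reached 5% gave type I error of 5.7%, 6.3% and 7.1% at ρ = 0, 0.3 and 0.5. The plan does not say that the more favourable result will be used. The figures show only what that freedom could cost, for one covariate.

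**The case against.** The strongest reply is that adjustment is already planned. The sentence after the t-test brings in an ANCOVA that tests the treatment difference with covariates, and an adjusted MMRM follows; baseline is not excluded. This stands. A reader might infer that the plan gives up about 9 power points on height and 8 on pain, but the documents do not support that. It would require that the unadjusted test decides the endpoint, or that baseline is left out of the ANCOVA, and neither is stated. It would also require ρ = 0.5, which is an assumption. The outcome is already scaled by baseline, so ρ could be small, and at 0.1 adjustment costs slightly more than it returns.

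A reader might also argue for a large ρ from the dosing table, since dose rises less than in proportion to lipoma size. That table is by diameter, whereas the endpoint is height, and no relation between the two is given. Any such gradient could act only in the active arm: with ρ = 0.5 there, 0 in the placebo arm and equal variances, the pooled value is 0.25, worth about 2.3 points for height before the finite-sample factor. It also pulls against measurement error in the denominator: error makes a high measured baseline go with a larger percent reduction, while a lower dose relative to size would go with a smaller one. For pain, the table says nothing.

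Lastly, randomisation keeps the unadjusted difference unbiased, and power exceeds 80% without adjustment. Both points stand. The margin for height is thin, since one fewer patient per arm gives 79.9%, but that is not a shortfall in the plan as written.

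What the reply does not answer is that the covariates are unnamed and chosen from the outcome data, and that no deciding analysis is designated.

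**Conclusion.** The point holds as a conditional gain in efficiency and as an avoidable data-driven choice. Over ρ from 0.1 to 0.5, with the finite-sample factor, adjustment changes power by −0.8 to +8.5 points for height and −0.7 to +7.1 for pain. These figures rest on the plan's own differences and SD, full follow-up of 19 per arm, and a linear relation with the same slope in both arms. Where in the range the trial lies cannot be settled from the documents. The lack of a named covariate and of a deciding analysis does not depend on ρ.

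**What to change.** Before unblinding, state in 10.2.1 that the deciding analysis is a patient-level ANCOVA of the mean percent reduction in height at Day 84 over the patient's injected lipomas, on treatment plus the patient's mean baseline height. In 10.2.2 do the same for pain, with the patient's mean baseline pain score. Keep the covariate whatever its p-value, and do not select these terms from the outcome data. Retain the t-test or Wilcoxon test as sensitivity analysis.

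The cost is SAP wording, one degree of freedom and a linear common-slope assumption. If ρ is near zero, the loss is about 1 power point (1.2 for height and 1.0 for pain at ρ = 0). No new data or patients are needed.
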